We hypothesize that sedation breaks down the functional hierarchy by prolonging the brain's intrinsic timescales (increase the TRWs; Fig. 1). This disrupts the functioning of large-scale brain networks that support perceptual integration. To test this hypothesis, we will measure the TRWs from resting-state (intrinsic) and music listening (extrinsic) periods during both conscious wakefulness and sedation. We anticipate observing a global prolongation of intrinsic TRWs, where the enlarged TRWs act as a low-pass filter of extrinsic sensory inputs, and cause the failure of high-order information integration over longer timescales (e.g. in prefrontal regions) during sedation.

[figure not shown]

Fig. 1. Hierarchical organization of temporal receptive windows (TRWs) and their measurement during wakefulness and sedation. During wakefulness, music is processed via hierarchical TRWs in the brain, where the timescales of neural responses (frequencies in Hz) to stimuli are matched with the multiple timescales of sensory stimuli. During sedation, the TRWs are enlarged such that they act as a low-pass filter or sparse sampling of the sensory inputs. The mismatch between the brain's TRWs and the timescales of sensory inputs may not only affect information acquisition at relatively short timescales but may also fail high-order information integration over longer timescales in, for instance, prefrontal regions with long TRWs.

Number of Subjects, Recruitment and Informed Consent

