1) SPGR high-resolution images. T1 weighted spoiled gradient recalled echo (SPGR) images will be acquired for high spatial resolution of anatomical images with parameters: 170 sagittal slices, 1.0mm thickness (no gap), TR=8.1s, TE=3.7ms, flip angle=8°, FOV=24cm, image matrix 256×256.

2) Functional MRI images. A gradient-echo EPI pulse sequence will be employed to acquire functional images over the whole brain with parameters: 28 slices, TR/TE=800/25ms (multiband fMRI acquisition), slice thickness=4mm, in-plane resolution=3.4×3.4mm; MB factor=4; field of view (FOV)=220mm, flip angle=76°, image matrix: 64×64. Verbal instructions were presented through earphones. Eight fMRI scans (16-min per scan) will be conducted throughout the experiment. The eight scans will include 16-min resting-state and 16-min music-listening during wakefulness baseline; 16-min behavioral test during propofol induction; 16-min resting-state and 16-min music-listening after loss of behavioral responsiveness; 16-min behavioral test during emergence period (after propofol infusion is terminated); 16-min resting-state and 16-min music-listening after recovery of behavioral responsiveness. There will be a 1-5 minute break in between scans. The imaging protocols and data acquisition will be completed within 2.5 hours scanning session for each subject.

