fMRI Protocol. During the rest-state period, participants will be asked to lay at rest with eyes closed, while trying to stay awake without thinking of anything in particular, and trying not to move. During the music presentation period, participants will be asked to listen to the music, keeping their eyes closed, try not to move, and stay awake. Four types of music, including Jazz, Rock, Pop and Country, will be presented in a pseudo-randomized order. We will select well-known music excerpt and being evaluated by all participants using familiarity and meaningful scales before the experiment. Each piece of music will be edited into 2-min duration. During the behavioral test period, participants will be asked to squeeze an MRI compatible grip dynamometer (a rubber ball) for every 10-second periods (96 cycles in total). The beginning of each cycle will be cued with the spoken word “squeeze”.

The verbal instructions will be programmed using E-Prime 3.0 (Psychology Software Tools, Pittsburgh, PA) and delivered via an audiovisual stimulus presentation system designed for an MRI environment. The volume of the headphones will be adjusted for subject comfort during wakefulness. The volume will be increased to 150% after loss of responsiveness. Behavioral responses will be measured in mmHg of air pressure during squeezing the rubber ball, using BIOPAC (<https://www.biopac.com>) MP160 system with AcqKnowledge software (V5.0). By comparing the timing of “squeeze” instructions (expected motor response) and the actual motor response during and after stepwise propofol infusion, the periods during which a subject loses of responsiveness (LOR), and recovery of responsiveness (ROR) will be determined. The onsets of LOR and ROR were defined at the time of first failure to squeeze, and the first success to squeeze, respectively.

All testing will be performed by the attending anesthesiologists. Spontaneous respiration, end-tidal CO₂, heart rate, and electrocardiogram will be continuously monitored. Noninvasive arterial pressure will be measured with magnetic resonance (MR)-compatible automatic monitor (BIOPAC). Post anesthesia care will consist of checking vital signs for 1 hour by the nursing staff. A wheelchair will be provided to assist the participant if needed. An anesthesiologist will be present during the entire duration of the study.

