Primary outcome measure: Blood Oxygen Level Dependent (BOLD) Response to sensory stimuli during sedation (timeframe: baseline to 90 minutes).

Secondary outcome measure: Squeeze Pressure, defined as measurement of force of participants' hand squeezing on a rubber ball in response to instructions (timeframe: baseline to 90 minutes).

Data Analysis

Image analysis will be conducted using AFNI (<http://afni.nimh.nih.gov/afni>). 1) The first two frames of each fMRI run will be discarded; 2) Slice timing correction; 3) Rigid head motion correction/realignment within and across runs; frame-wise displacement (FD) of head motion will be calculated using frame-wise Euclidean Norm (square root of the sum squares) of the six-dimension motion derivatives. A frame and its each previous frame will be tagged as zeros (ones, otherwise) if the given frame's derivative value has a Euclidean Norm above FD=0.5 mm; 4) Coregistration with high-resolution anatomical images; 5) Spatial normalization into Talairach stereotactic space; 6) Using AFNI's function 3dTproject, the time-censored data will be high-pass filtered above 0.008 Hz. At the same time, various undesired components (e.g., physiological estimates, motion parameters) will be removed via linear regression. The undesired components include linear and nonlinear drift, time series of head motion and its temporal derivative, binarized FD time series (output data included zero values at censored time points), and mean time series from the white matter and cerebrospinal fluid; 7) Spatial smoothing with 6 mm full-width at half-maximum isotropic Gaussian kernel; 8) The time-course per voxel of each run will be normalized to zero mean and unit variance, accounting for differences in variance of non-neural origin (e.g., distance from head coil).

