The music evoked activity, will be quantified by inter-subject correlation (inter-SC) of the fMRI responses (7), depends systematically on the music structure coherence. For instance, early auditory areas respond reliably to low-level acoustic features of music, whereas frontal areas process long-timescale musical structures, on the order of minutes. This analysis provides a measure of the reliability of the responses through the functional hierarchy by comparing the BOLD response time courses across different subjects. The inter-SC analysis will be performed on a voxel-by-voxel basis. First, the Pearson product-moment correlation will be computed between a voxel's fMRI time course in one individual and the average of that voxel's fMRI time courses in the remaining subjects. Next, the average correlation coefficient will be calculated at every voxel. Finally, it will produce an average inter-SC map during music presentation period. Statistical significance of inter-SC for each state (i.e. wakefulness baseline, LOR period, and ROR period) and the difference between states (e.g. wakefulness baseline vs. LOR period) will be assessed using a phase-randomization procedure (forming a null distribution).

Intrinsic TRWs will be calculated from the resting-state data. We will use Mean Frequency (MF) of fMRI signal fluctuations to index the TRW length (8). Specifically, power spectrum will be obtained by computing the periodogram of each voxel time series using AFNI program 3dPeriodogram. Tapering was applied using the Hamming window to reduce bias and error variance for spectral estimation in finite data (9). The MF of a spectrum will be calculated as the sum of the product of the spectrogram power intensity and the frequency, divided by the total sum of spectrogram power intensity:

$$MF = \frac{\sum_{i=0}^n P_i F_i}{\sum_{i=0}^n P_i}$$

where n is the number of frequency bins in the spectrum, F_i is the frequency of spectrum at bin i of n, and P_i is the power intensity of spectrum at bin i of n. Lower MF indicates a shift toward a longer timescale or slower dynamics.

Anticipated Results and Implications

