We expect to find a spatial hierarchy with reliable responses (inter-SC) to music starting in the primary auditory cortex and adjacent areas of auditory cortex (A1+), processing along the superior temporal sulcus (STS) and further up to the middle and inferior frontal gyrus during conscious wakefulness. We anticipate that during LOR, inter-SC in especially the frontal areas, which process long-timescale musical structures, will be reduced. We also expect to observe that, during

LOR, the intrinsic timescales derived from the resting-state are overall prolonged, and the intrinsic functional gradient of hierarchy is also shrunk. The degree of the intrinsic TRW prolongation and the degree of the functional gradient shrinkage may show a negative correlation with the spatial extension of inter-SC during sedation.

Together, the results should advance our understanding of how the brain processes information at increasing levels of abstraction along the functional hierarchy, and how this information processing may be altered during sedation. The information gained should add further insight into the neural mechanisms for temporal integration in the brain supporting conscious experience of complex stimuli and their degradation under sedation.

Power Analysis

For an fMRI study of cognitive function, Desmond and Glover (10) reported that about 25 subjects are necessary to achieve 80% power for a 0.5% increase of activity. We also conducted power analysis based on our previous study with graded sedation of propofol (11). The average Cohen's d as a measure of the effect size was 0.56. For 80% power and alpha=0.05, N=24 human subjects will be needed. The obtained subject number is also very close to the suggested optimal group size for reliable statistics in functional MRI studies (12). To account for possible failure or attrition, we plan for 30 as the maximum number of subjects.

Biological Variables

We will recruit participants of both sexes with various ethnic/racial backgrounds, aiming for diversity and equal representation. The age range will be limited to 18-40 years in order to limit age-dependent variation in anesthetic requirement for sedation and for participant safety.

Potential Risks

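### Excerpts of 2 min and a 125 s high-pass filter do not match the minutes-long musical structure to which the plan ties frontal inter-subject correlation; a second, lower cutoff should be pre-specified and the claim limited to about 2 min.

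*Combined protocol and SAP*

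**What the plan says.** Rationale and Hypothesis predicts that sedation prolongs the brain's intrinsic timescales and that the enlarged temporal receptive windows (TRWs) "cause the failure of high-order information integration over longer timescales (e.g. in prefrontal regions) during sedation". Data Analysis gives the scale of the structure involved: early auditory areas follow low-level acoustic features, "whereas frontal areas process long-timescale musical structures, on the order of minutes". Anticipated Results and Implications expects that during LOR "inter-SC in especially the frontal areas, which process long-timescale musical structures, will be reduced".

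The stimulus is set under Procedures, fMRI Protocol: "Four types of music, including Jazz, Rock, Pop and Country, will be presented in a pseudo-randomized order", and "Each piece of music will be edited into 2-min duration". Under Imaging, "Eight fMRI scans (16-min per scan) will be conducted throughout the experiment", three of them music runs (wakefulness, LOR, recovery).

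In Data Analysis step 6, "the time-censored data will be high-pass filtered above 0.008 Hz", with drift, motion and tissue signals regressed out at the same time. Inter-SC is then computed voxel by voxel, and its significance is assessed within each state and between states. Intrinsic TRWs come from the resting-state runs only.

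**The concern.** The prediction concerns slow, long-timescale processing. The stimulus contains no musical structure longer than 2 min, and the preprocessing removes BOLD fluctuations slower than 125 s before inter-SC is measured. The plan does not reconcile these choices with the minutes-long scale it assigns to frontal areas.

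Two things are at stake. The first is interpretation: a frontal loss could be reported as failed integration over minutes when nothing beyond 2 min was presented. The second is a possible bias between states. The plan itself predicts slower dynamics under sedation. If responses shared across subjects slow during LOR, more of their variance falls below the cutoff in LOR than in wakefulness. Inter-SC could then drop partly because the filter removed the slowed signal, and this would be read as lost integration.

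**Working it through.** **Inputs from the documents.** Piece length is 2 min = 120 s (fMRI Protocol). The cutoff is 0.008 Hz (Data Analysis step 6). A run lasts 16 min = 960 s, and TR is 0.8 s (Imaging). The frontal timescale is given only as minutes, with no figure.

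**Inputs assumed.** Pieces play back to back and fill the run, the filter is ideal, and the integrator receives white input. The response models below are illustrations and do not come from the documents.

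**Arithmetic on the plan's own figures**

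- Cutoff period: 1/0.008 = 125 s.
- Frames per run: 960/0.8 = 1,200. Frequency spacing: 1/960 = 0.00104 Hz.
- Pieces per run, if back to back: 960/120 = 8.
- One cycle per piece: 1/120 = 0.00833 Hz. This is bin 8 of 600, the first one kept. The filter removes bins 1 to 7.
- A 240 s cycle (0.0042 Hz) is removed completely.
- At 0.004 Hz (250 s) only bins 1 to 3 are removed, so the band with periods from 960/7 = 137 s to 960/4 = 240 s is recovered.

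**Share of a response's variance that survives the filter**

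| Illustrative response | Kept at 0.008 Hz | Kept at 0.004 Hz |
|---|---|---|
| Ramp over 2 min, identical in every piece | 100% | 100% |
| Ramp over 2 min, slope differing by piece | about 34% | about 85% |
| Linear integrator, 30 s window | 55% | 76% |
| Linear integrator, 60 s window | 24 to 28% | 55 to 64% |
| Fast response, gain building up over the piece (time constant 60 s) | 93% | 97% |

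For an integrator with window T, the share kept is the integral of sinc²(fT) from the cutoff to 0.625 Hz, divided by the same integral from 0. The lower figure for the 60 s window uses this formula. The upper one comes from simulated 960 s runs, where the run mean is removed first. The 30 s row uses the formula only. The ramp and gain rows are from simulated runs.

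**Effect of slowing during LOR.** Suppose the shared window lengthens from 30 s to 60 s. The share kept falls from 55% to 24% at 0.008 Hz, leaving 24/55 = 44% of the earlier share. At 0.004 Hz it falls from 76% to 55%, leaving 55/76 = 72%. The lower cutoff reduces the filter's contribution but does not remove it.

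**What these shares are not.** They are not changes in inter-SC. The filter also removes slow noise, and the documents give no signal-to-noise figure from which an inter-SC value could be derived.

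**The case against.** The strongest reply is that a TRW is not a BOLD period. Rationale and Hypothesis defines it as the stretch of earlier input that can affect a response. A long-window region may respond quickly in a way that depends on context, and such responses pass the filter almost intact (93% in the model above). This stands. The documents do not say which response model applies to frontal cortex. They do, however, index timescale by the mean frequency of the BOLD signal at rest, which makes the slow-response case relevant.

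A reader might infer more: that the design cannot test its frontal hypothesis at all, or that frontal inter-SC sits at a floor when awake, so that a low value in LOR would be uninterpretable. The documents do not support either reading. Structure of 1 to 2 min is present and can count as minutes, and a full 120 s cycle passes the filter. Inter-SC is assessed for significance in wakefulness itself, so a frontal region that the music did not drive would be visible there.

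One might also count only the time during which a single piece fills a region's whole window. With 2-min pieces, (120 − W)/120 gives 50%, 25% and 0% for windows of W = 60, 90 and 120 s. That is an all-or-nothing rule. The average share of the window filled by the current piece, 1 − W/(2 × 120), is 75%, 62.5% and 50%. Both assume back-to-back pieces, and neither predicts inter-SC.

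Finally, the intrinsic-timescale part of the hypothesis is measured at rest, so piece length does not affect it.

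**Conclusion.** The concern holds in a limited form. The frontal comparison between wakefulness and LOR remains testable. What the plan cannot support is a statement about musical structure beyond about 2 min, because none is presented. The 0.008 Hz cutoff may also remove most of the slow, piece-specific signal near that limit: about 34% of piece-specific ramps and 24 to 28% of a 60 s integrator is kept. Because the plan expects slowing under sedation, some of an observed inter-SC loss could come from the filter.

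The 2 min and 125 s figures follow directly from the documents. The retained shares depend on the assumed models, the back-to-back layout and the ideal filter. Under the fast-response model the filter matters little. The documents do not settle which case applies, so the analysis should show whether the result depends on the cutoff.

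A loss seen at both cutoffs is necessary for the long-timescale interpretation but does not prove it. No scrambled or coherence-graded music is described that would isolate timescale.

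**What to change.** In Data Analysis, pre-specify for the three music runs a second inter-SC analysis with the high-pass cutoff at about 0.004 Hz. Keep the drift regressors and the 0.008 Hz result. State in advance that a frontal loss will be called failed long-timescale integration only if it holds at both cutoffs.

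In Data Analysis and in Anticipated Results and Implications, limit the claim to musical structure up to about 2 min.

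The cost is one extra filter setting, analysis time and wording. The downside is more low-frequency drift in the second analysis, which is why it should sit beside the 0.008 Hz result and not replace it. A lower cutoff cannot restore structure that the stimulus lacks.

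Longer excerpts, for example four 4-min pieces in the same 16-min run, are an optional trade-off and not a required change. They would allow longer structure to be probed. They would also give fewer distinct pieces, and with one piece per genre the effects of piece and genre could not be separated.

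### Only 1.6 s is dropped at run start, so a shared run-onset response can register as inter-subject correlation if music runs are correlated in a common order

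*Combined protocol and SAP*

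**What the plan says.** Procedures, Imaging, item 2 specifies the functional acquisition as "TR/TE=800/25ms (multiband fMRI acquisition", and adds: "Eight fMRI scans (16-min per scan) will be conducted throughout the experiment". Data Analysis, step 1, reads: "The first two frames of each fMRI run will be discarded". The later steps are a 0.008 Hz high-pass filter, regression on drift, motion, the censoring series and mean white-matter and CSF signals, smoothing, and scaling of each run to unit variance. No lead-in, run-onset regressor or further trimming is described.

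Inter-SC is the Pearson correlation "between a voxel's fMRI time course in one individual and the average of that voxel's fMRI time courses in the remaining subjects", averaged over subjects at each voxel so that "it will produce an average inter-SC map during music presentation period". Significance within each state, and of differences between states, "will be assessed using a phase-randomization procedure (forming a null distribution"). Resting-state runs are used only for the mean-frequency measure.

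Under fMRI Protocol, the music comes in 2-minute pieces in pseudo-randomized order. The section does not say whether all subjects share that order, or whether runs are re-aligned by piece before correlation.

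**The concern.** Inter-SC picks up anything that happens at the same time in every subject. The start of scanner noise, and any arousal it causes, is such an event, and the response to it outlasts 1.6 s. Phase randomization keeps each time course's spectrum but destroys its timing. It therefore spreads a brief onset response over the whole run, and the null does not contain the shared event. The share of frames affected is a poor guide to the harm, because the null distribution of a mean correlation is very narrow.

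Two planned readings could be touched. One is the set of inter-SC maps, including the spatial extent of inter-SC that Anticipated Results and Implications proposes to relate to timescale prolongation. The other is the contrast of wakefulness with loss of responsiveness (LOR). A transient of equal size in both states would partly cancel. One that weakens under sedation would look like the expected loss of inter-SC.

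**Working it through.** The plan gives no discard time in seconds and no onset amplitude, so there is no figure of its own to reproduce.

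**1. Discard time.** Inputs: 2 frames (Data Analysis), repetition time 0.8 s and 16-minute runs (Imaging, item 2).
- Discarded: 2 × 0.8 = 1.6 s.
- Frames per run: 960 / 0.8 = 1,200, so 1,198 are kept and 2 / 1,200 = 0.17% is removed.

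**2. Does another step remove the transient?** The filter cut-off corresponds to a period of 1 / 0.008 = 125 s, so a 10-20 s response passes. White-matter and CSF regression was tested in the simulation below. Regressors carrying 25% to 100% of the transient still left about 97% of voxels significant at a 2 SD peak. Their noise was simulated as independent of the voxel.

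**3. Is it an approach to magnetic steady state?** The excess signal at frame k, counted from 0, is (1−M)/M × (E1 cos 76°)^k, with E1 = exp(−0.8/T1) and M = (1−E1)/(1−E1 cos 76°). The flip angle is in the document; the T1 values are assumed. At the first retained frame (k = 2):
- Grey matter, T1 1.3 s: E1 = 0.540, M = 0.529, excess 0.8915 × 0.1307² = 1.5%.
- Grey matter, T1 1.6 s: 2.5%.
- CSF, T1 4 s: 13%.

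One frame later grey matter is below 0.4%. Two frames largely deal with this effect in grey matter, so the slower haemodynamic or arousal response is the one that matters.

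**4. Simulation.** From the plan: 25 subjects, 1,198 frames, 0.008 Hz high-pass with drift removal, unit-variance scaling, leave-one-out r averaged over subjects, phase-randomized null. Assumed: coloured noise, no music signal, a haemodynamic-shaped onset transient with a between-subject amplitude coefficient of variation of 50%, and all runs correlated in acquisition order. There were 150 voxels per setting. The Monte Carlo standard error near 5% is √(0.05 × 0.95 / 150) = 1.8 points.

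With no transient, 4-7% of voxels were significant at one-sided p<0.05, so the test is calibrated. The null SD of mean inter-SC was about 0.011, which puts the p<0.05 threshold near 1.645 × 0.011 = 0.018. With 1.6 s discarded:

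| Peak (voxel SD) | Mean inter-SC | Significant, p<0.05 | Significant, p<0.001 |
|---|---|---|---|
| 0.5 | 0.006 | 15% | 1% |
| 1 | 0.014 | 39% | 1-6% |
| 1.5 | 0.028 | 79% | 35% |
| 2 | 0.051 | 99% | 84-89% |
| 3 | 0.096 | 100% | 100% |

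Check by hand at 1 SD: (0.018 − 0.014) / 0.011 = 0.36, an upper tail of about 36%, against 39% simulated.

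**5. Sensitivity to assumptions.**
- Shape: at a 1 SD peak, other assumed shapes and durations gave p<0.05 rates from 9% (single frame) and 11% (exponential decay, 6 s time constant) up to 70% (a half-sine).
- Order: if each subject hears the pieces in a different order and segments are re-aligned before correlation, the rates at 1, 2 and 3 SD fall to 5%, 21% and 43%.

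**6. How much trimming is enough?** Each cell shows p<0.05 / p<0.001:

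| Peak | 1.6 s | 10.4 s (13 frames) | 20 s (25 frames) |
|---|---|---|---|
| 1 SD | 39% / 1-6% | 8% / 1% | 7% / 0% |
| 2 SD | 99% / 84-89% | 31% / 2% | 8% / 0% |
| 3 SD | 100% / 100% | 69% / 31% | 7% / 1% |

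About 20 s returns the rate to near nominal for this shape; about 10 s does not.

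**The case against.** The strongest reply is that the amplitude decides the result and the documents do not give one, least of all for voxels that do not respond to music. At 0.5 SD the inflation is modest, and below that it approaches nominal. This stands: the percentages describe assumed transients, not this trial's data.

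Second, if music begins with the run, the first sound is music. The primary outcome is the BOLD response to sensory stimuli, so a response to music onset is a true response and should not be counted as artefact. This also stands. The concern is limited to scanner-noise and arousal onset, and trimming will cost some genuine early response. An onset response is still not the tracking of musical structure over minutes that Data Analysis attributes to frontal areas.

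Third, the plan states neither a common music order nor a voxel threshold. A different order per subject with re-alignment dilutes the effect strongly, though not to zero at 2-3 SD. A stricter threshold nearly removes it at 1 SD but not at 2 SD. Without a stated threshold and multiplicity correction, no map-level error rate can be computed.

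A reader might infer from the 99-100% rows that the planned maps would be mostly false, or that a fall in inter-SC at LOR would be an artefact. The documents support neither. They give no onset amplitude, and they do not show that the transient differs between states. Headphone volume is raised to 150% after LOR, so onset conditions are not identical, but that does not establish the direction or size of any difference.

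**Conclusion.** The point holds in limited form. The plan removes 1.6 s per run, has no other step against a run-onset response, and tests inter-SC against a null that does not contain one. A shared transient can therefore produce significant inter-SC in voxels that do not track the music.

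This rests on three conditions: runs are correlated in a common order, the transient peaks at roughly 0.5-1 voxel SD or more, and the voxel threshold is lenient or the peak is large. Under the assumed haemodynamic shape, uncorrected one-sided p<0.05 and a common order, the share runs from about 15% at 0.5 SD to 99% at 2 SD. The effect on the state contrast was reasoned, not simulated; it matters only if the transient changes with sedation. This is a worthwhile refinement, not a defect that undermines the study.

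**What to change.** For the inter-SC analysis, drop about the first 25 frames (25 × 0.8 = 20 s) of each music run before filtering and normalisation, and report the untrimmed result as a sensitivity analysis. State whether the music order is common to all subjects and, if it is not, how segments are aligned.

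Also compute inter-SC on the resting-state run in each of the three states and show it beside the music maps as a negative control. It should be near zero. It can reveal scan-start effects but not a response to the first sound, so it complements the trimming and does not replace it.

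The cost is 25 / 1,200, about 2% of frames per music run, some genuine early music response, and one extra run of the same script. No new data or change to subject procedures is needed.
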